### 5.3.2 Secondary Outcome Measures

• Lung function measured by spirometry, the principal component will be the change in FEV1 from baseline to week 8\*.

Participant compliance measured by total number of tablets administered as a proportion of total number of tablets supplied.

\*In light of the COVID19 lockdown lung function will not be measured in order to prevent unnecessary risk of exposure to study participants.

\*\* Blood samples will no longer be taken in order to prevent unnecessary risk of exposure to study participants.

## 5.3.3 Exploratory Outcomes

#### **Clinical Exploratory Outcomes**

• Symptoms measured by CAT score and EQ-5D-DL from baseline to week 8

#### **Biological Exploratory Outcomes**

- Neutrophil activation biomarkers that may include but are not limited to measurement of neutrophil elastase and ICAM-1.
- Inflammatory response biomarkers that may include but are not limited to measurement of proteins, metabolites, cytokines (including but not limited to TNFα, IL-1β, IL-6, IL-8), proteases and anti-proteases.
- Nucleic acid analysis in sputum and blood including, viral/bacterial nucleic acid detection and gene expression. RNA sequencing, mRNA analysis and methylation analysis.

### 5.4 Exploratory Bronchoscopy Sub-study

EViSCO trial participants will be recruited to the sub-study on a voluntary basis and will indicate their consent to have a bronchoscopy at baseline and following 8 weeks treatment during the initial study visit. Participants undergoing bronchoscopy will have bronchial washings and tissue specimens taken via bronchial biopsies and brushings. This will allow bronchial epithelial cell culture and pathological assessment of the airway epithelium before and after treatment.

### 5.4.1 Exploratory Bronchoscopy Sub-study Outcome Measures

- Measurement of epithelial ICAM-1 and airway neutrophilic inflammatory markers.
- Bronchial biopsy histology and immunohistopathology.
- Indices of nucleic acid expression in sputum and blood including viral and genomic DNA, viral RNA, microRNA and mRNA analysis & methylation analysis.

## 5.5 Proposed Study Milestones

The study will be conducted over four years. There will be a 9-month set up period to allow regulatory applications, site set up and training. Patient recruitment has been estimated at 4 patients per month over a period of 22 months. As there is an 8-week (2 months) treatment period and 4 weeks (1 month) follow up, it is anticipated that patient recruitment and follow up will be completed within a 25-month period. Analysis of the primary and secondary outcomes and dissemination of the study results will take place following trial completion. The projected trial milestones are shown below in Table 1.

Year	1		2			3			4							
Quarter	1	2	3	4	1	2	3	4	1	2	3	4	1	2	3	4
Management meetings	х	х	х	х	х	х	х	х	х	х	х	х				
Trial set up	х	х	х													
Ethical approval			х													
Trial staff recruitment & training	х	х	х													
Drug source & label	х	х	х													
Patient recruitment				х	х	х	х	х	х	х	х					
Follow up, monitoring & review				х	х	х	х	х	х	х	х	х				
Data cleaning & analysis													х	х		
Dissemination															х	х

## Table 1 EViSCO Trial Milestones

## 5.6 Study Duration

The estimated duration of the study will be four years.

## 5.7 End of Study

The trial will end when 88 study participants have completed the 12-week follow-up and database closure occurs for the final study analysis. The trial will be stopped prematurely if:

- Mandated by the Research Ethics Committee (REC)
- Mandated by the Medicines & Healthcare products Regulatory Agency
- Mandated by the Sponsor (e.g. following recommendations from the Data Monitoring and Ethics Committee (DMEC)
- Funding for the trial ceases

The REC that originally gave a favourable opinion of the trial and the MHRA who issued the Clinical Trial Authorisation (CTA) will be notified in writing once the trial has been concluded or if terminated early.

## 6 PATIENT SELECTION CRITERIA

Eligibility to participate in the trial will be confirmed by a medically qualified person who is named on the delegation log and documented on the eligibility checklist. Patients will be eligible to participate in the study if they fulfil all of the following inclusion criteria and none of the exclusion criteria.

## 6.1 Inclusion Criteria

- 1. Age over 18 years.
- Clinical diagnosis of COPD as defined by the Global Initiative for Chronic Obstructive Lung Disease criteria (FEV1/FVC <70%) with GOLD 2 and GOLD 3 airflow obstruction (FEV1 30-80% predicted) with significant symptoms
- 3. Presence of Epstein-Barr virus on sputum PCR analysis.

### 6.2 Exclusion Criteria

- 1. Respiratory failure (defined as long-term oxygen therapy).
- 2. An acute exacerbation of COPD in the previous month (defined as an acute, sustained worsening of symptoms that is beyond normal day-to-day variations).
- 3. A diagnosis of asthma.
- 4. Patients with known hypersensitivity to valaciclovir or aciclovir.
- 5. Patients unable to swallow study drug capsules.
- 6. Established diffuse interstitial lung disease (e.g. Idiopathic Pulmonary Fibrosis).
- 7. Established diagnosis of symptomatic bronchiectasis\*.
- 8. Patients known to be pregnant or breastfeeding.
- 9. Patients with an estimated creatinine clearance less than 50ml/minute\*\*.
- 10. Known participation in investigational medicinal product trials within 30 days.
- 11. Patients who do not adequately understand verbal or written information.
- 12. Concomitant use of nephrotoxic medicinal products or medicines associated with altered renal tubular secretion. These inlcude aminoglycosides, organoplatinum compounds, methotrexate, pentamidine, foscarnet, ciclosporin, tacrolimus,tenofovir, cimetidine and probenecid. As iodinated contrast used in radiological examinations can be nephrotoxic any patients with planned radiological contrast studies will be deferred for a reasonable time until after their contrast.
- For the exploratory bronchoscopy sub-study patients will require adequate oxygen saturations, FEV1 >0.5 L and will not be performed while patients are taking aspirin or clopidogrel (BTS guidelines 2013).

\* Patients with a primary respiratory diagnosis of established symptomatic bronchiectasis will be excluded. In order to fulfil this exclusion criteria patients must exhibit the clinical bronchiectasis phenotype and demonstrate computed tomography (CT) evidence of established multi-lobar bronchiectasis.

\*\* Documented eGFR values from within the past 4 months will be used to confirm eligibility. If not available screening U&E will be completed.

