## 9.7 Study Drug Administration

Patients will take valaciclovir 1 gram (2 x 500mg capsules) or matching placebo capsules orally three times daily for 8 weeks .

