### 10.1.2 Visit 1 (Baseline) Procedures

Medical history, medication history, vital signs and BMI will be recorded at the baseline visit. Participants will complete CAT and EQ-5D-5L assessments.. FBC, research blood and sputum samples will be taken. Participants will be asked regarding exacerbation status and if applicable exacerbations will be documented. Four weeks supply of the study drug or placebo will be given and an appointment for follow up will be made. The GP will be informed via written correspondence. Substudy volunteers will undergo diagnostic bronchoscopy.

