### 10.2.6 Pharmacy (prescribing, randomisation and dispensing)

Prescriptions must not be signed prior to eligibility being confirmed. The date that the prescription form is signed (i.e. requested) cannot be prior to date on which eligibility is confirmed. the date of study drug dispensed by Pharmacy is the randomisation date. The eligibility checklist and stickers cannot be signed off until all results of the tests required to confirm eligibility are completed and available. The study drug start date cannot be before prescription pick up date and must be accurately recorded as this relates to study drug compliance.

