### 8.2 Baseline Characteristics

- Gender, n(%) by treatment arm
- Age(years), mean(SD) by treatment arm
- Height(m), mean(SD) by treatment arm
- Weight(kg), mean(SD) by treatment arm
- BMI(kg/m^2), mean(SD) by treatment arm
- Transfer Factor((TLCO) as a percentage of the predicted value(%)), mean(SD) by treatment arm
- Forced Expiratory Volume(FEV1 (L)), mean(SD) by treatment arm
- Forced Vital Capacity(FVC (L)), mean(SD) by treatment arm
- FEV1/FVC Ratio (%), mean(SD) by treatment arm
- Mid Expiratory Flow (MMEF 25-75% (L/s)), mean(SD) by treatment arm
- Peak Expiratory Flow(PEF (L/s)), mean(SD) by treatment arm
- Smoking Status, n(%) by treatment arm
- Pack Years, mean(SD) by treatment arm
- Presence of EBV, n(%) by treatment arm
- Quantitative PCR Titre(copies), mean(SD) by treatment arm
- Co-morbidities, n(%) by treatment arm
- Pre-existing Cardiovascular issues, n(%) by treatment arm
- Any exacerbations in past 12 months, n(%) by treatment arm

- Number of exacerbations in past 12 months, n(%) by treatment arm
- Number of exacerbations in past 12 months requiring steroids, n(%) by treatment arm
- Number of exacerbations in past 12 months requiring antibiotics, n(%) by treatment arm
- Number of exacerbations in past 12 months resulting in hospitalization, n(%) by treatment arm

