**APPENDIX 1: EXAMPLE DRAFT SUMMARY TABLES, FIGURES AND LISTINGS**

**Figure A1. The CONSORT Diagram**

**Table x.x: Reason for Exclusion From the Study**

Total number of patients screened		n
Total number of patients recruited		n
Total number of patients excluded		n
Reasons for Exclusion	The patient is not over 18 years of age?	n
	The patient does not have a clinical diagnosis of COPD	n
	The patient does not display the presence of Epstein-Barr virus on sputum PCR analysis?	n
	Respiratory failure (defined as long-term oxygen therapy).	n
	An acute exacerbation of COPD in the previous month	n
	A diagnosis of asthma.	n
	Patient has known hypersensitivity to valaciclovir or aciclovir.	n
	Patient unable to swallow study drug capsules.	n
	Established diffuse interstitial lung disease (e.g. Idiopathic Pulmonary Fibrosis).	n
	Established diagnosis of symptomatic bronchiectasis.	n
	Patient known to be pregnant or breastfeeding.	n
	Patient has an estimated creatinine clearance less than 50ml/minute.	n
	Patient is known to have participated in investigational medicinal product trials within 30 days.	n
	Patient does not adequately understand verbal or written information.	n
	Concomitant use of nephrotoxic medicinal products or medicines associated with altered renal tubular secretion.	n
Other	n	

Table x.x: Baseline Characteristics at Trial Entry

Baseline Characteristics		Treatment Group		Total
		Valaciclovir	Placebo	
		N	n	
Gender	Male	n (%)	n (%)	n (%)
	Female	n (%)	n (%)	n (%)
Age (years)		xx.x (xx.x)	xx.x (xx.x)	xx.x (xx.x)
Height(m)		xx.x (xx.x)	xx.x (xx.x)	xx.x (xx.x)
Weight(kg)		xx.x (xx.x)	xx.x (xx.x)	xx.x (xx.x)
BMI(kg/m2)		xx.x (xx.x)	xx.x (xx.x)	xx.x (xx.x)
Transfer Factor((TLCO) as a percentage of the predicted value(%))		xx.x (xx.x)	xx.x (xx.x)	xx.x (xx.x)
Forced Expiratory Volume(FEV1 (L))		xx.x (xx.x)	xx.x (xx.x)	xx.x (xx.x)
Forced Vital Capacity(FVC (L))		xx.x (xx.x)	xx.x (xx.x)	xx.x (xx.x)
FEV1/FVC Ratio (%) ,		xx.x (xx.x)	xx.x (xx.x)	xx.x (xx.x)
Mid Expiratory Flow (MMEF 25-75% (L/s))		xx.x (xx.x)	xx.x (xx.x)	xx.x (xx.x)
Peak Expiratory Flow(PEF (L/s)),		xx.x (xx.x)	xx.x (xx.x)	xx.x (xx.x)
Smoking Status	Current Smoker	n (%)	n (%)	n (%)
	Ex-Smoker	n (%)	n (%)	n (%)
	Never Smoked	n (%)	n (%)	n (%)
Pack years		xx.x (xx.x)	xx.x (xx.x)	xx.x (xx.x)
Presence of EBV	Yes	n (%)	n (%)	n (%)

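### The renal exclusion is set as creatinine clearance below 50 ml/minute but checked with eGFR, and neither document says how the two relate

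*Protocol*

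**What the plan says.** Protocol 6.2, criterion 9, excludes "Patients with an estimated creatinine clearance less than 50ml/minute". The footnote to that criterion reads "Documented eGFR values from within the past 4 months will be used to confirm eligibility", with a screening U&E if no value is available. SAP 1.4 repeats the criterion and the footnote. The exclusion table in SAP Appendix 1 records the reason as "Patient has an estimated creatinine clearance less than 50ml/minute".

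Neither document names an equation for clearance or eGFR, gives an eGFR limit, or states an equivalence. A footnote to the schedule of assessments (Protocol Table 2, SAP Table 1) lets the researcher repeat the screening U&E if older values look borderline, but gives no conversion to clearance.

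Everyone who passes gets the same dose (Protocol 9.7): "Patients will take valaciclovir 1 gram (2 x 500mg capsules) or matching placebo capsules orally three times daily". No renal dose adjustment is stated. Under the current protocol, visits 2 and 3 are telephone contacts with a sputum sample (10.1.3, 10.1.4), so no renal blood test is scheduled during treatment.

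**The concern.** The criterion and its check use different quantities. Under the usual equations, creatinine clearance in mL/min rises with body weight, while eGFR as laboratories report it is scaled to a standard body surface and takes no account of weight. In a light older person, the same creatinine can give a clearance below 50 and an eGFR well above it. An investigator who follows the footnote exactly could then admit someone whom the criterion excludes.

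The stake is patient safety and uniform application of a safety limit. The authors treat renal function as a safety matter: criterion 12 separately excludes nephrotoxic drugs and drugs that alter tubular secretion. With no renal blood test scheduled on treatment, the entry check carries more weight. The randomised comparison is not at stake, because Protocol 8.1 requires eligibility to be confirmed before 1:1 allocation.

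**Working it through.** The documents give no derived renal figure to reproduce. What can be tested is whether the two measures can fall on opposite sides of 50 in an admissible patient. Protocol 6.1 sets no upper age limit, and neither document sets a weight limit.

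**From the documents:** limit 50 ml/minute, not per 1.73 m²; check by eGFR.

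**Assumed:** the equations and the patients. Scr is creatinine in mg/dL, that is µmol/L ÷ 88.4.

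- Cockcroft-Gault clearance = (140 − age) × weight × 1.04 (women) or 1.23 (men) ÷ creatinine in µmol/L.
- CKD-EPI 2009 = 141 × min(Scr/k, 1)^a × max(Scr/k, 1)^−1.209 × 0.993^age, × 1.018 for women; k = 0.7 and a = −0.329 (women), k = 0.9 and a = −0.411 (men).
- CKD-EPI 2021 = 142 × min(Scr/k, 1)^a × max(Scr/k, 1)^−1.200 × 0.9938^age, × 1.012 for women; same k, a = −0.241 (women) or −0.302 (men).
- MDRD = 175 × Scr^−1.154 × age^−0.203, × 0.742 for women.
- De-indexed eGFR = eGFR × BSA ÷ 1.73, with BSA = 0.007184 × height^0.725 × weight^0.425 (DuBois; cm, kg).

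**Woman, 75 y, 50 kg, 80 µmol/L**

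- Clearance: 65 × 50 × 1.04 ÷ 80 = 42.3.
- eGFR: 62.1 (CKD-EPI 2009), 66.2 (CKD-EPI 2021), 60.7 (MDRD).
- De-indexed at heights of 150 to 165 cm: about 50 to 59. For example, at 158 cm BSA is 1.487, and 62.1 × 1.487 ÷ 1.73 = 53.4.
- Weight at which clearance equals 50: 50 × 80 ÷ (65 × 1.04) = 59.2 kg. Below that, clearance is under the limit and the indexed eGFR is unchanged.

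**Man, 78 y, 52 kg, 90 µmol/L**

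- Clearance: 62 × 52 × 1.23 ÷ 90 = 44.1.
- eGFR: 70.2, 75.4 and 70.8 in the same order.
- De-indexed at 165 to 175 cm: about 63 to 71.
- Weight at which clearance equals 50: 50 × 90 ÷ (62 × 1.23) = 59.0 kg.

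**How far this extends.** Fix the CKD-EPI 2009 value at 60. Clearance is then below 50 at weights under about 58 kg (woman of 70), 61 kg (woman of 75), 62 kg (man of 70) and 65 kg (man of 75). At average weight the measures agree: for a woman of 65 y, 70 kg, 80 µmol/L, clearance is 75 × 70 × 1.04 ÷ 80 = 68.3 and eGFR is 62 to 71.

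Removing the indexing narrows the gap. It brings the woman close to the limit, but it does not bring either patient below 50.

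**The case against.** The strongest reply is that the footnote is the working definition: it is attached to criterion 9 and says what confirms eligibility, so eGFR below 50 is what was meant. On that reading nobody is wrongly admitted and only the wording is at fault. The documents do not rule this out, but they do not settle it either, since the SAP exclusion table again says clearance.

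The second reply is that a medically qualified person confirms eligibility (Protocol 6), may repeat a borderline U&E, and is free to calculate clearance. Much of this stands. A reader might infer that the repeat test could not help, but the documents leave the judgement of borderline to the researcher, and the woman above, at about 50 to 59 de-indexed, could well prompt a second look. The man, at 63 to 71, probably would not. A repeat U&E also brings no rule for comparing the result with a clearance limit.

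A reader might also infer the opposite error, heavy patients wrongly excluded. That depends on using the indexed eGFR, whereas the criterion is in ml/minute. Take a man of 62 y, 100 kg, 140 µmol/L, with clearance 78 × 100 × 1.23 ÷ 140 = 68.5. His eGFR of 44.5 to 49 rises to about 54 to 62 when de-indexed at 170 to 180 cm, and he passes. That error is not claimed here.

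**Conclusion.** Minor, and worth correcting because it is cheap. The mismatch in the text is certain. Its effect on patients is conditional: if clearance is meant as written, some light older patients with clearance of about 42 to 44 can pass on an eGFR of 61 to 75 indexed, or about 50 to 71 de-indexed.

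These figures rest on assumed equations and invented patients. The documents give no ages, weights or creatinine values, so the number affected cannot be derived, and it is zero if eGFR below 50 was intended. A reader might go further and infer that unsuitable patients were enrolled or harmed. Nothing in the documents shows that, and they do not say what risk this dose carries at a clearance in the low forties.

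No endpoint, estimate or power figure changes. Other protections remain: stopping on safety grounds (Protocol 9.8), adverse-event contacts at weeks 4, 8 and 12, and DMEC review (15.2). They act after entry and do not make the check match the criterion.

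**What to change.** For patients screened from now on, keep the documented eGFR or screening U&E as the source and add a clearance calculation to the footnote in Protocol 6.2 and SAP 1.4, for example:

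> Before the prescription is signed, Cockcroft-Gault clearance (mL/min) will also be calculated from the creatinine behind the eGFR or from the screening U&E, with age, sex and actual body weight. Weight is taken at screening or at Visit 1. The patient is excluded if either the clearance or the reported eGFR is below 50.

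Excluding on either measure means that nobody with a low eGFR is newly admitted. Reword the exclusion row in SAP Appendix 1 to match. The Protocol's amendment summary refers to remaining study visits, so some patients were apparently enrolled already; the SAP should describe how they were actually screened and not apply the new rule to them in retrospect. Changing only the wording would tidy the text but would not add the safety check.

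The cost is small. Body size is already recorded at Visit 1 ("Medical history, medication history, vital signs and BMI will be recorded at the baseline visit"), and SAP 8.2 already lists "Weight(kg), mean(SD) by treatment arm". Protocol 10.2.6 already holds the process until the checks are complete: "Prescriptions must not be signed prior to eligibility being confirmed", and "The eligibility checklist and stickers cannot be signed off until all results of the tests required to confirm eligibility are completed and available". There are two downsides. A few more patients will fail screening, in a number that cannot be estimated. Also, Protocol Table 2 places eligibility at screening and BMI at Visit 1, so either a weight is added at screening or part of the eligibility check moves to Visit 1. The proposal assumes that the creatinine behind a documented eGFR can be retrieved; if not, the screening U&E supplies it.

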## 7 PATIENT SCREENING AND CONSENT

## 7.1 Screening Procedure

Potentially eligible subjects with COPD will be identified and screened by members of the direct care team based on the inclusion/exclusion criteria as specified in the study protocol (section 6). Eligible subjects will receive REC approved written study information sheets and have the opportunity to review this document in advance of the consent process. An appropriately trained doctor within the study team will seek informed consent from eligible participants following their routine scheduled clinic appointment. Appropriate signatures and dates must be obtained on the informed consent documentation prior to collection of trial data and administration of the trial drug. If no consent is given a patient cannot be randomised into the trial. At the screening visit, an appropriately trained doctor within the study team will discuss the study with the patient to determine their interest in participating and address any queries the patient may have. Informed consent, screening sputum and blood samples (if required) will be obtained at this initial screening visit. The Northern Ireland Clinical Trials Unit (NICTU) will provide screening logs which will be completed by the Chief Investigator (CI) or designee to document all patients screened for the study. Patients screened and not recruited on to the study should also be documented on the screening log, including the reason for not being enrolled on the trial. Sites will be required to submit screening data to the CTU monthly.

## 7.2 Informed Consent Procedure

The study will be performed in accordance with the ethical principles that have their origin in the Declaration Helsinki. The Chief Investigator is responsible for ensuring that informed consent for trial participation is given by each patient. An appropriately trained doctor or nurse may take consent. Signatures and dates must be obtained on the informed consent documentation prior to collection of trial data and administration of the trial drug. If no consent is obtained a patient cannot be randomised into the trial. The patient will be informed about the trial by the responsible clinician or a member of the trial team and given a copy of the Patient Information Sheet. Informed patients will be given an adequate amount of time to consider their decision on trial entry. If the patient decides to enter the trial, they will be asked to sign two copies of the Patient Consent Form, which will be countersigned by the responsible doctor or designee. The patient will retain one copy of the signed consent form. The second copy will be photocopied and the photocopy will be placed in the patient's medical records, while the original will be retained in the Investigator Site File. Study participant's GPs will be informed via written letter when they are randomised.

## 7.3 Withdrawal of Consent

Patients may withdraw or be withdrawn from the trial at any time without prejudice. Data recorded up to the point of withdrawal will be included in the trial analysis. If a patient requests termination of the trial drug during the treatment period, the study drug will be stopped, but the patient will continue to be followed-up as part of the trial. If a patient withdraws consent during trial treatment, the trial drug will be stopped, but permission will be sought to access medical records for data related to the trial.

## 8 RANDOMISATION

## 8.1 Randomisation Procedure

Eligible participants will be randomised using a 1:1 allocation ratio into the two groups. All researchers will be blinded to the sequence. After informed consent has been obtained and eligibility has been confirmed, the next sequential number on the randomisation schedule will be assigned to the patient as the unique patient identifier.

The pharmacist will also confirm the study pack numbers to be dispensed at visit 1 and visit 2.

